5.3 General Concomitant Medication and Supportive Care Guidelines

No other approved or investigational anticancer treatment will be permitted during the study period, including chemotherapy, biologic response modifiers, or immunotherapy. Palliative-intent single-fraction radiation therapy after cycle 1 is permissible at the PI's discretion, but may not be administered concurrently with LMP744. A delay of up to one week prior to starting a subsequent cycle of treatment will be permitted to enable marrow recovery. No medications, including over-the-counter products, should be started without first consulting with the investigator.

5.3.1 Vomiting

Anti-emetics will not be administered prophylactically for the first dose, only for subsequent doses if nausea or emesis occurs. However, if a patient develops nausea/vomiting, anti-emetics, such as Ondansetron will be instituted prior to treatment. If nausea or emesis persists, a second agent such as olanzapine or lorazepam should be added.

5.3.2 Diarrhea

Patients will not be given anti-diarrheal prophylactically. If a patient develops diarrhea, if clinically indicated a test for C. difficile will be ordered. If a patient is found to have C. difficile colitis, appropriate antibiotics will be instituted. If noninfectious diarrhea

develops and does not have an identifiable cause other than study drug administration, anti-diarrheal (such as diphenoxylate HCl 2.5 mg + atropine sulfate 0.025 mg/tablet) dosed according to package insert or loperamide 4 mg PO after the first unformed stool with 2 mg PO every 2 hours as long as unformed stools continue (4 mg every 4 hours while asleep). No more than 16 mg of loperamide should be taken in during a 24-hour period. This regimen can be repeated for each diarrheal episode. Diarrhea will be considered refractory if it does not resolve within 48 hours to Grade 2 with the above suggested regimens.

5.3.3 Neutropenia

Febrile neutropenia is a life-threatening complication and urgent broad-spectrum antibiotics, as well as an aggressive search for the source and microbial cause of the episode.

Growth factors to prevent neutropenia will not be administered prophylactically. If necessary, they may be administered according to accepted American Society of Clinical Oncology (ASCO) guidelines to allow re-treatment.

5.3.4 Anemia

Symptomatic anemia should be treated with red blood cell infusion, which is recommended if the hemoglobin falls below 8 g/dL. The initiation of erythropoietic therapy for the management of chemotherapy-induced anemia follows the American Society of Hematology/ASCO clinical practice guidelines.

5.3.5 Thrombocytopenia

Thrombocytopenia will be treated conservatively. In the absence of bleeding, fever, or a necessary invasive procedure, platelet transfusions should be given for a platelet count $\leq 10,000/\text{mm3}$. If invasive procedure(s) is (28) planned, or the patient develops bleeding, platelet transfusions should be administered in accordance with the standard of practice, usually maintaining a platelet count above 50,000/mm³.

5.3.6 Tumor lysis syndrome

At the discretion of the PI, patients at risk of tumor lysis will receive allopurinol 24 hours prior to the initiation of therapy. Additional measures such as hospitalization with aggressive iv hydration, use of rasburicase, and urinary alkalization will be used at the discretion of the investigator.

5.3.7 Allergic Reaction

If a patient develops hives or swelling, the LMP744 infusion will be held and at a minimum diphenhydramine administered at a dose of 50 mg IV. Other medications (such as steroids or epinephrine) can be used at the discretion of the clinician. Once the reaction has subsided, patients may be rechallenged with the original dose of LMP744. In case the reaction does not subside within 2 hours or the patient develops a subsequent reaction on rechallenge, the study drug will be discontinued and the patient taken off study. A grade ≤ 2 allergic reaction will not be considered a DLT; pre-medication will be added to treatment on subsequent dosing if patients experience \leq grade 2 infusion

reaction.

- 5.3.8 Inhibitors and Inducers of ABCG2 and P-gp LMP744 is a substrate for ATP-binding cassette transporter protein ABCG2 and P-gp. Unless medically necessary, avoid the use of strong inhibitors and inducers of these transporters.
- 5.3.9 Cytochromes P450 Inhibitors and Inducers, and Inhibitors of Drug Transporters The pathways by which LMP744 is eliminated are not known. Unless medically necessary, avoid the use of strong inhibitors and inducers of all major drug metabolizing enzymes and drug transporters.

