5.2 Definition of Dose-Limiting Toxicity

- 5.2.1 Grade \geq 3 non-hematologic toxicity will be considered dose limiting, with the following exceptions:
 - 5.2.1.1 Grade 3 fatigue lasting \leq 7 days.

5.2.1.2 Grade 3 diarrhea will only be considered dose limiting if, after 48 hours, it is refractory to treatment as outlined in Section 5.3.2. Grade 4 diarrhea will be dose limiting.

5.2.1.3 Grade 3 nausea and vomiting will be considered dose limiting after 48 hours if it is refractory to maximal anti-emetic therapy and unable to be corrected to Grade 1 or baseline. Grade 2 nausea or vomiting after 72 hours despite three anti-emetogenic agents will also be considered dose limiting.

5.2.1.4 Grade 3 rise in creatinine, not corrected to Grade 1 or baseline after intravenous fluids within 24 hours, will be considered dose limiting. All Grade 4 rises in creatinine will be dose limiting.

5.2.1.5 Grade 3 electrolyte toxicities unable to be corrected to Grade 2 or baseline within 24 hours will be considered dose limiting.

5.2.2 Grade 4 hematological toxicity will be considered dose limiting if it meets the criteria below. Lymphopenia (any grade) will not be considered dose limiting for all

subjects.

- 5.2.2.1 Neutropenia: Grade 4 neutropenia for >5 days without fever or infection will be considered dose limiting. Grade 4 neutropenia of any duration accompanied by fever or infection will be considered dose limiting. Twice weekly blood draws will be needed (after onset of grade 4 neutropenia) to monitor duration of neutropenia for the first 2 cycles. On subsequent cycles (cycle 3 and beyond), weekly blood draws will be monitored at the onset of grade 4 neutropenia.
- 5.2.2.2 Thrombocytopenia: Grade 4 thrombocytopenia will be considered dose limiting. Grade 3 thrombocytopenia associated with bleeding will be considered dose limiting.
- 5.2.2.3 Anemia: Grade 4 anemia will be considered dose limiting.
- 5.2.3 Any neurotoxicity Grade ≥ 2 that is not reversible to a Grade ≤ 1 within 2 weeks will be considered dose limiting.
- 5.2.4 Any non-hematologic Grade 2 toxicity that does not resolve to Grade ≤1 or baseline within 14 days despite adequate treatment as described in Section 5.3 will be considered dose limiting, except for alopecia.

Management and dose modifications associated with the above adverse events are outlined in Section 6.

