6.1 Drug-related toxicity

- 6.1.1 If a patient has a DLT during cycle 1, no further treatment will be administered for that cycle and the dose will be reduced by one dose level for the next cycle.
- 6.1.2 If the patient has a DLT during any subsequent cycle, no further treatment will be administered for that cycle and the dose will be reduced by one dose level for the next cycles and the patient will not be eligible for intra-patient dose escalation.
- 6.1.3 If Grade 3 diarrhea occurs (increase of >6 stools/day over baseline) but resolved to ≤ grade 2 with anti-diarrheal within 72 hours, the patient will receive the same dose on subsequent cycles with anti-diarrheal treatment as stated in Section 5.3.2. If Grade ≥3 diarrhea continues > 72 hours despite treatment, this constitutes a DLT (see Section 5.2) and LMP744 will be dose reduced by one dose level for subsequent cycles.

| Diarrhea grade after 72 hours of anti-diarrheal med | Management/Next Dose for LMP744 | |
|---|--|--|
| \leq Grade 1 | No change in dose | |
| Grade 2 | Resume at same dose level. | |
| Grade 3 | Hold [*] until \leq Grade 2. Resume at one dose level lower, if refractory. ^{**} | |
| Grade 4 | | |
| *Patients requiring a delay of >2 weeks will be taken off protocol therapy. | | |
| **Patients requiring > two dose reductions will be taken off protocol therapy. | | |
| Recommended management: Loperamide antidiarrheal therapy | | |
| Dosage schedule: 4 mg at first onset, followed by 2 mg with each loose motion until diarrhea-free for | | |
| 12 hours (maximum dosage: 16 mg/24 hours) | | |
| Adjunct anti-diarrheal therapy is permitted and should be recorded when used. | | |

6.1.4 If Grade ≥2 nausea and vomiting require anti-emetics, the patient will receive antiemetics prior to the administration of subsequent doses of LMP744 as described in Section 5.3.1.

| Nausea grade after 72 hours of antiemetic support | Management/Next Dose for LMP744 | |
|--|---|--|
| \leq Grade 1 | No change in dose | |
| Grade 2 | Resume at same dose level. | |
| Grade 3 | Hold [*] until \leq Grade 2. Resume at one dose level lower if refractory. ^{**} | |
| Grade 4 | Off protocol therapy | |
| * Patients requiring a delay of >2 weeks will be taken off protocol therapy. | | |
| **Patients requiring > two dose reductions will be taken off protocol therapy. | | |
| Recommended management: antiemetics. | | |

| Vomiting grade after 72 hours of antiemetic support | Management/Next Dose for LMP744 | |

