6.2 Intra-patient Dose Escalation and De-escalation

Intra-patient dose ESCALATION is permitted ONLY if:

- 1. Patients did not experience toxicity >Grade 1 that is possibly, probably, or definitely related to the study drug after one cycle at the initial dose level (subsequent cycles may be delayed up to 14 days past the end of the previous cycle of 28 days to allow for toxicities to resolve).
- 2. Higher doses have been evaluated and completed without a DLT.
- 3. The patient's disease has not progressed.
- 4. There is no concern of cumulative toxicity.

Doses may be escalated by one dose level for every subsequent cycle, provided conditions 1-4 are met, up to the last evaluated dose level NOT associated with DLT.

If a patient experiences DLT during a cycle, the dose will be REDUCED by one level (if there is a lower dose level, see Section 5.1.2) for the next cycle, provided toxicity has recovered to \leq Grade 1 within 14 days after completing a 28-day cycle, and the patient's disease is stable or responding. If a patient is dose reduced twice and still experiences a DLT, then the patient would be removed from the study. If no lower dose level exists, then the patient will be removed from the study.

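### Sections 5.3.7 and 6.1.6 permit rechallenge at the original dose after an allergic reaction of any grade, which the DLT rules forbid at Grade ≥3

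*Combined protocol and SAP*

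**What the plan says.** Section 5.3.7 is triggered by hives or swelling, with no grade attached. The infusion is held and diphenhydramine given. The paragraph also covers more serious treatment: "Other medications (such as steroids or epinephrine) can be used at the discretion of the clinician". It continues: "Once the reaction has subsided, patients may be rechallenged with the original dose of LMP744". Drug is stopped for good only if the reaction has not subsided within 2 hours or a further reaction follows rechallenge. The closing sentence says that a Grade ≤2 reaction is not a DLT and that pre-medication is added for later doses after such a reaction. Section 6.1.6 has the same trigger, the same permission and the same limits.

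The DLT rules are separate. Section 5.2.1 says that Grade ≥3 "non-hematologic toxicity will be considered dose limiting, with the following exceptions". The five exceptions are fatigue, diarrhea, nausea and vomiting, creatinine, and electrolytes. After a cycle 1 DLT, Section 6.1.1 says "no further treatment will be administered for that cycle and the dose will be reduced by one dose level for the next cycle". Section 6.1.2 covers later cycles: "If the patient has a DLT during any subsequent cycle, no further treatment will be administered for that cycle", again with a one-level reduction. Section 6.2 repeats the reduction: "If a patient experiences DLT during a cycle, the dose will be REDUCED by one level".

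**The concern.** Allergic reaction is not among the exceptions in Section 5.2.1, and Sections 5.3.7 and 6.1.6 exempt only Grade ≤2. A Grade ≥3 reaction is therefore a DLT, and the plan gives two incompatible instructions on what may follow it. A clinician who wishes to re-expose a patient at full dose after a severe reaction can cite two paragraphs in support, while a third rule forbids it.

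What is at stake is patient safety in the expansion cohort, which Amendment L opened at 190 mg/m²/day. The protocol treats hypersensitivity as foreseeable. Section 2.3 reports allergic reactions in the earlier dog studies and facial swelling at 5 mg/kg/day (100 mg/m²/day) in the definitive one, and says such reactions may occur. Section 5.1 requires at least 1 hour of observation after dosing in cycle 1. The signal is preclinical: the CAEPR in Section 7.1.1 (version 1.3) lists no allergic, hypersensitivity or infusion reaction in patients.

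**Working it through.** The plan states no figure to reproduce. The check sets the rules side by side for one case and then sizes the difference in dose.

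**The case: Grade ≥3 hives or swelling that subsides within 2 hours**

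| Question | Sections 5.3.7 and 6.1.6 | Sections 5.2.1, 6.1.1, 6.1.2 and 6.2 |
|---|---|---|
| Is it a DLT? | Only Grade ≤2 is exempted | Yes; not among the exceptions |
| More drug in the same cycle? | Permitted at the original dose | None |
| Dose in the next cycle? | Original dose permitted | One level lower |

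Sections 5.3.7 and 6.1.6 give no timing for rechallenge. In the same cycle it breaks the bar on further treatment; in the next cycle it breaks the one-level reduction. No timing satisfies both.

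**Is there a stated precedence?** Section 5.2 ends with a pointer: "Management and dose modifications associated with the above adverse events are outlined in Section 6". Section 6 contains both rules (6.1.1 and 6.1.2 on one side, 6.1.6 on the other), so the pointer does not settle the matter. For diarrhea the link is made explicitly. Section 6.1.3 says of Grade ≥3 diarrhea persisting despite treatment: "this constitutes a DLT (see Section 5.2) and LMP744 will be dose reduced by one dose level for subsequent cycles". Section 6.1.6 has no equivalent step for Grade ≥3 reactions.

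**Size of the difference at 190 mg/m²/day** (level 6; the next level down is 96 mg/m²/day, from the table in Section 5.1.1)

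- Same cycle. If the reaction starts before any of Day d's dose is infused, the dose still available under 5.3.7 is (6 − d) × 190. This gives 950, 760, 570, 380 and 190 mg/m² for Days 1 to 5. Under 6.1.1 or 6.1.2 it is 0. These are upper bounds, since drug infused before the reaction reduces them.
- Next cycle. 5 × 190 = 950 mg/m² against 5 × 96 = 480 mg/m². The difference is 470 mg/m² and the ratio is 190/96 = 1.98.

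**How often.** The documents give no rate. If a fraction p of patients has a Grade ≥3 reaction, the chance of at least one among n patients is 1 − (1 − p)^n.

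| Assumed p | n = 15 | n = 6 |
|---|---|---|
| 1% | 1 − 0.99^15 = 0.140 | 1 − 0.99^6 = 0.059 |
| 5% | 1 − 0.95^15 = 0.537 | 1 − 0.95^6 = 0.265 |

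Fifteen is the planned expansion size and a ceiling, because Section 13.1 stops expansion accrual at 6 usable paired biopsies; 6 patients is the smallest number that could supply them. Only some of these reactions would involve hives or swelling, settle within 2 hours and be rechallenged.

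**The case against.** The strongest reply is that the text can be read consistently. The closing sentence of 5.3.7 and 6.1.6 speaks of Grade ≤2 when it sets out DLT status and later pre-medication, so rechallenge could be taken to apply to those grades only. Rechallenge is also optional, whereas the DLT rules are mandatory, and a permission need not override a prohibition. No site is ever required to do two incompatible things.

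The second part is true: a site that withholds drug complies with everything. The first part requires a grade limit that the rechallenge sentence does not contain. The trigger has no grade, and 5.3.7 provides for epinephrine, so it is not worded for mild reactions alone. A reader who lets the specific rule prevail over the general one would follow 6.1.6, which is the less safe result. Read literally, that reader would also find no pre-medication requirement after a Grade ≥3 reaction, because the requirement is stated only for Grade ≤2.

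Several points about size stand. The 1% to 5% rate is an assumption, and the resulting probabilities are for any Grade ≥3 reaction, not for the conflict itself. The 950 mg/m² same-cycle figure is the extreme case. The dog dose is not shown to be a threshold, since reactions occurred at other doses and infusion rates, so its ratio to the trial dose (190/100 = 1.9) is illustrative only. Post-dose observation, serious adverse event reporting, weekly patient review and a safety monitoring committee all reduce the practical risk. None of them changes what the text authorizes.

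**Conclusion.** The concern holds. For a Grade ≥3 reaction with hives or swelling that subsides within 2 hours, two paragraphs authorize re-exposure that the DLT management rules forbid, and nothing says which governs. At 190 mg/m²/day the rules differ by at most 950 mg/m² in the same cycle and by 470 mg/m² in the next. Both figures assume that the clinician chooses to rechallenge and that no reaction recurs.

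Such events are probably uncommon, and their frequency cannot be determined from the documents. No study result is affected: the event remains a DLT under 5.2.1 whatever rechallenge shows, and escalation is complete, so the MTD stands. This should be fixed because it is a direct safety contradiction that is cheap to remove. The conclusion rests on the wording alone and not on the assumed rates.

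**What to change.** In both 5.3.7 and 6.1.6, replace the rechallenge sentence with wording such as:

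> If the reaction is Grade ≤2 and settles within 2 hours, LMP744 may be restarted at the same dose with the pre-medication specified below. A Grade ≥3 allergic or infusion reaction is a DLT. The patient receives no more drug in that cycle and is then managed under 6.1.1 or 6.1.2, or permanently discontinued.

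Keep the existing off-study rule, at any grade, for reactions that last beyond 2 hours or recur on rechallenge. The sponsor should also state when permanent discontinuation applies instead of a one-level reduction, because the documents do not show that a lower dose makes re-exposure after a severe reaction safe.

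The cost is a short wording change in two paragraphs at the next amendment, with no new procedure. A few patients whose Grade 3 reaction settles quickly would lose the rest of that cycle and, if they continue, receive 96 instead of 190 mg/m²/day in the next one. Sections 6.1.1 and 6.1.2 already require this.

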5.4 Duration of Therapy

In the absence of treatment delays due to adverse events, treatment may continue until one of the following criteria applies:

- Disease progression
- Intercurrent illness that prevents further administration of treatment
- DLT recurs after two dose reductions for DLT or no lower dose level exists (as described in Sections 5.1 and 6.2)
- Patient decides to withdraw from the study
- Noncompliance at the discretion of the PI

5.5 **Duration of Follow Up**

Patients will be followed for 30 days after the last dose of study drug is administered or until one of the following occurs: patient enrolls on another protocol, patient receives standard of care, or death, whichever comes first. The follow-up will consist of a phone call between Days 27-30 after the last dose to evaluate adverse events that were ongoing and any new events that might be deemed related to the therapy. Unacceptable toxicities (i.e., AEs related to the intervention) that have not resolved by Day 30 post-treatment will be followed via biweekly phone calls until stabilization or resolution.

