5.6 Criteria for Removal from Study

Patients will be removed from study for one of the following reasons: completed 30-day followup period, toxicities are unresolved but stabilized, patient enrolls on another protocol, or patient receives other type of treatment-intent therapy. The reason for study removal and the date the patient was removed must be documented in the medical record.

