7.3.3 Expedited Reporting Guidelines

Use the NCI protocol number and the protocol-specific patient ID assigned during trial registration on all reports.

Note: A death on study requires both routine and expedited reporting, regardless of causality. Attribution to treatment or other cause must be provided.

Death due to progressive disease should be reported as **Grade 5 "Disease Progression"** in the system organ class (SOC) "General disorders and administration site conditions." Evidence that the death was a manifestation of underlying disease (e.g., radiological changes suggesting tumor growth or progression: clinical deterioration associated with a disease process) should be submitted.

Phase 1 and Early Phase 2 Studies: Expedited Reporting Requirements for Adverse Events that Occur on Studies under an IND/IDE within 30 Days of the Last Administration of the Investigational Agent/Intervention ^{1, 2}

| FDA REPORTING REQUIREMENTS FOR SERIOUS ADVERSE EVENTS (21 CFR Part 312) NOTE: Investigators MUST immediately report to the sponsor (24) ANY Serious Adverse Events, whether or not they are considered related to the investigational agent(s)/intervention (21 CFR 312.64) An adverse event is considered serious if it results in ANY of the following outcomes: Death A life-threatening adverse event An adverse event that results in inpatient hospitalization or prolongation of existing hospitalization for ≥ 24 hours A persistent or significant incapacity or substantial disruption of the ability to conduct normal life functions A congenital anomaly/birth defect. Important Medical Events (IME) that may not result in death, be life threatening, or require hospitalization may be considered serious when, based upon medical judgment, they may jeopardize the patient or subject and may require medical or surgical intervention to prevent one of the outcomes listed | | |
|--|--------------------------------|-------------------------|
| in this definition. (FDA, 21 CFR 312.32; ICH E2A and ICH E6). ALL SERIOUS adverse events that meet the above criteria MUST be immediately reported to the NCI via electronic submission within the timeframes detailed in the table below. | | |
| Hospitalization | Grade 1 and Grade 2 Timeframes | Grade 3-5 Timeframes |
| Resulting in Hospitalization \ge 24 hrs | 10 Calendar Days | 24-Hour 5 Calendar Days |
| Not resulting in Hospitalization ≥ 24 hrs | Not required | |

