7.5 NCI Clinical Director Reporting

Problems expeditiously reported to the OHSRP/IRB in iRIS will also be reported to the NCI Clinical Director. A separate submission is not necessary as reports in iRIS will be available to the Clinical Director.

In addition to those reports, all deaths that occur within 30 days after receiving a research intervention **s**hould be reported via email to the Clinical Director unless they are due to progressive disease.

To report these deaths, please send an email describing the circumstances of the death to the Clinical Director/designee at [contact] within one business day of learning of the death.

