13. STATISTICAL CONSIDERATIONS

13.1 Study Design/Endpoints

The primary objective of this trial is to establish the safety, tolerability, and MTD of LMP744 administered intravenously daily for 5 days in 28-day cycles, to patients with refractory solid tumors. This study will follow design 3 of the Simon accelerated titration designs (26), with dose escalation proceeding in 1-patient cohorts and switching to standard 3+3 dose escalation of dose levels when specific criteria are met (Section 5.1.1). (*Note: As of Amendment G* [10/18/18], the study switched to standard 3+3 dose escalation. As of Amendment I [9/25/19], there is flexibility to accrue up to an additional 3 patients on any dose level that has 1 DLT observed among 6 patients [see Section 5.1.2.1]. As of Amendment L [date 6/7/2021], the MTD has been identified and the expansion cohort will begin accrual [see Section 5.1.2.2].)

Following this, another 15 patients will be treated at the MTD on an expansion cohort, which will include mandatory biopsies. With 15 patients and a tumor biopsy QA criteria failure rate of 50% with respect to paired (pre- and post-dose) biopsies, we have an 85% likelihood of having at least 6 usable PD samples, and 95% likelihood of having at least 5 usable samples from the expansion cohort. Biopsy tissue quality will be monitored and accrual to the expansion phase will stop once we have obtained 6 usable paired samples. With 6 PD sample pairs, there is 90% power to detect a treatment effect equivalent to 1.85 SD's (associated with the intra-patient baseline variability of the PD marker) with the paired 2-sample T-test, at the 1-sided .05 significance level, for a given PD variable of interest. PD variables may be log-transformed to achieve more nearly normal distributions.

DLTs will be summarized descriptively according to dose level. In addition, the relation of dose level with presence or absence of DLT will be analyzed using logistic regression, as described by Simon (20).

All AEs will be tabulated by type and grade according to dose level. In addition, the presence or absence of grade 2 or higher toxicity for each patient in each treatment cycle will be modeled using random effects logistic regression as described by Simon (20), incorporating dose during the cycle and total dose for previous cycles, with intra-patient random effects.

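### The early-stop rules for safety follow-up in Sections 5.5 and 5.6 differ, and neither matches the 30-day serious-event window of Section 7.3.3

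*Combined protocol and SAP*

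**What the plan says.** Section 5.5 opens with a fixed period: "Patients will be followed for 30 days after the last dose of study drug is administered". It then allows an earlier end, "until one of the following occurs: patient enrolls on another protocol, patient receives standard of care, or death, whichever comes first". The follow-up is one phone call on days 27-30, covering adverse events still ongoing and "any new events that might be deemed related to the therapy". Related toxicities unresolved at day 30 are followed by further calls until they stabilize or resolve.

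Section 5.6 lists the reasons for removal from study. Besides completed follow-up and stabilized toxicity, these are "patient enrolls on another protocol, or patient receives other type of treatment-intent therapy".

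Section 7.3.3 governs expedited reporting for the 30 days after the last administration. Investigators must report any SAE "whether or not they are considered related to the investigational agent(s)/intervention". A death on study is reportable whatever its cause. A footnote extends reporting past day 30 for SAEs with at least a possible attribution. Section 7.5 adds an email report for "all deaths that occur within 30 days after receiving a research intervention", but exempts deaths from progressive disease.

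On analysis, Section 13.1 states: "All AEs will be tabulated by type and grade according to dose level". It gives no collection window. It also plans a random-effects logistic model of grade 2 or higher toxicity by patient and cycle.

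**The concern.** Safety and tolerability are part of the primary objective. The MTD has been declared and the expansion cohort is accruing, so the adverse-event tables at that dose are a main product of what remains of the trial.

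A site that follows Section 5.5 as written may stop looking before the window in Section 7.3.3 closes. Even when it looks, it asks a narrower question than Section 7.3.3 poses. A site can report only what it learns.

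Early departure is also unlikely to be random. Progression ends treatment under Section 5.4, and patients who are deteriorating may well move to other care soonest. That is a plausible inference, not something the documents show. If it is right, the unobserved days fall where serious events are more likely.

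**Working it through.** The plan states no figure on this point, so there is none to reproduce. The check is a comparison of the sections, some day arithmetic and an illustration.

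**1. The rules side by side**

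| Section | When it ends | Which events |
|---|---|---|
| 5.5 | Day 30, or earlier at another protocol, standard of care (undefined) or death | Ongoing events; new ones that might be related |
| 5.6 | Follow-up completed, toxicities stabilized, another protocol, or other treatment-intent therapy | Not stated |
| 7.3.3 | Day 30; no early end for later therapy | All SAEs, related or not |
| 7.5 | Day 30; no early end for later therapy | Deaths not due to progressive disease |
| 13.1 | No window given | All adverse events |

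There are two separate gaps. The first is the early stop, which affects patients who start other care before day 30. The second is the content of the call, which affects everyone: an SAE judged unrelated is not asked about even in a patient followed for the full 30 days.

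There is a third, smaller conflict. Section 5.5 keeps following unresolved related toxicity, yet new therapy ends follow-up under 5.5 and removes the patient under 5.6. No order of priority is given.

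**2. Day arithmetic**

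Dosing is on days 1-5 of a 28-day cycle (Section 5).
- Days from last dose to cycle end: 28 − 5 = 23.
- The 30-day window ends on cycle day 5 + 30 = 35.
- Days beyond a completed cycle: 35 − 28 = 7, and 7/30 = 23% of the window.
- Last scheduled mid-cycle laboratory tests in cycles 1-3 are on day 15, which is 15 − 5 = 10 days after the last dose. In later cycles, laboratory tests are scheduled only at cycle start.

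For a patient who does not begin another cycle, the call is therefore the main scheduled look at the later part of the window.

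**3. One patient**

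Suppose a patient starts other care on day 10 after the last dose and is hospitalized on day 25. Under 5.5, follow-up ended on day 10 and no call is due. The unobserved part is 30 − 10 = 20 of 30 days (67%). The hospitalization is still reportable under 7.3.3. If the event is instead a death, it is unclear whether a patient already removed under 5.6 counts as on study.

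**4. Illustration of follow-up time lost**

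Let q be the share of patients who start other care before day 30, and t the day after the last dose on which they start. Share of follow-up time lost = q × (30 − t)/30. Both q and t are assumptions.

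| q | t | Calculation | Time lost |
|---|---|---|---|
| 10% | 28 | 0.10 × 2/30 | 0.7% |
| 30% | 21 | 0.30 × 9/30 | 9.0% |
| 50% | 14 | 0.50 × 16/30 | 26.7% |

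At the accrual ceiling of 53 patients (Section 13.2), the last row is 53 × 0.50 × 16 = 424 of 53 × 30 = 1,590 patient-days.

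These figures are time, not events. As a share of events they run high to the extent that sites hear of and report events anyway. They run low because a cancelled call would also have asked about the days before departure.

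**The case against.** The strongest reply is that Sections 7.3.3 and 7.5 are reporting duties, and nothing in 5.5 or 5.6 suspends them. That is correct. A reader might infer that 5.5 exempts late events from reporting; it does not. What remains is that the duty applies to events a site knows about, and the protocol removes or narrows the contact by which it would come to know.

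Second, *standard of care* beside enrollment on another protocol most naturally means other anticancer treatment. Supportive care is given throughout the study under Section 5.3, so a reading that lets it end follow-up is strained. On the natural reading, 5.5 and 5.6 largely agree. This stands, but the term is undefined, and the mismatch with 7.3.3 exists on either reading.

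Third, there are other safeguards. The study calendar has an adverse-event evaluation, examination and laboratory tests at progression, and the team reviews grading and attribution weekly during active treatment (Section 12.2). Restaging is every two cycles at first, so many departures would fall near cycle end, about day 23, leaving at most 7 days exposed. This makes the larger rows of the illustration less typical. It does not cover the days after the patient has gone.

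Four stronger readings are not supported:
- That Section 13.1 requires adverse events to day 30. It sets no window, and that omission is the gap there.
- That Section 7.5 needs every death. It exempts deaths from progressive disease.
- That a percentage of serious events is being lost. This needs assumed event risks and the further assumption that no event after departure is ever reported.
- That the MTD is in doubt. Section 5.1.2.1 bases escalation on cycle 1 dose-limiting toxicity, and Section 6.4.1 replaces patients who miss completing a cycle for reasons other than toxicity.

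**Conclusion.** The inconsistency is real and worth correcting. Sections 5.5 and 5.6 give two differing stop rules, and neither matches the 30-day SAE window of Section 7.3.3. The one scheduled follow-up contact can be cancelled early and asks for less than 7.3.3 requires. Late SAEs and deaths *can* therefore be under-counted; the documents do not show that they *are*.

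The size cannot be derived, because the plan gives neither the share of patients who move on early nor when they do so. The 0.7% to 26.7% range depends entirely on the assumed q and t. The effect falls on the descriptive safety tables and, to the extent that late events in a final cycle are missed, on the grade 2 or higher toxicity model.

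**What to change.** Reconcile Sections 5.5 and 5.6 with 7.3.3, and complete 13.1:

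1. Use one defined term for the new-therapy trigger in both 5.5 and 5.6.
2. Make the day 27-30 call for every dosed patient, including those who have started other therapy or joined another protocol.
3. On that call, ask for all SAEs and deaths up to 30 days after the last dose, regardless of attribution.
4. Record the start date and type of any later therapy.
5. State in 13.1 the collection window for the adverse-event tables, and flag events with onset after new therapy.

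Whether non-serious events are also collected after new anticancer therapy is a trade-off between completeness and confounded attribution. It can be left to the sponsor, provided the choice is written down.

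The cost is small: a wording amendment, a few extra calls within a contact that already exists, and some events after new therapy that are harder to attribute. The flag in step 5 deals with the last of these. No dose or treatment rule changes.
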